### **Subject Populations**

All subjects who receive at least one dose of Imm 124-E or placebo will be included in the safety analysis while those who receive at least 7 days of treatment will be considered for the primary pathophysiology-based endpoint

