**ENDPOINTS:**

*Mechanistic Endpoints:*

- The sample size is based on a decrease in plasma endotoxin levels (adjusting for baseline) as measured by analysis of covariance across the study groups. This was

chosen based on the mechanism of action of Imm 124-E. The hypothesis is that both active-drug groups are superior to placebo. In prior studies, we have found the standard deviation of endotoxin levels to be 8-10%

- markers of gut permeability
- intestinal inflammation (calprotectin)
- TNF- $\alpha$  and other immune-inflammatory markers
- microbiome-metagenome

*Efficacy related endpoints:*

- number of subjects meeting Lille failure criteria at day 7
- mortality at 30 days, 90 days and 180 days,
- time to drop in conjugated bilirubin by 50%
- change in MELD and sequential organ failure assessment scores and Discriminant Function
- serum bile acids
- liver function tests

*Safety related endpoints:*

- incidence and severity of gastrointestinal events, including nausea, vomiting and diarrhea
- Proportion of subjects who develop renal failure, encephalopathy or pulmonary compromise
- Frequency of sepsis
- Frequency of any other adverse events

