## INVESTIGATIONAL PLAN

### Overall Study Design and Plan – Description

**Figure 1: Study Schema**

Subjects with severe AH (MELD score  $\geq 20$  and  $\leq 28$ ) about to receive prednisolone (40 mg/day x 28 days) will be randomized to receive either:

- Group A: 2400 mg/day Imm 124-E as 1200mg bid PO
- Group B: 4800 mg/day Imm 124-E as 2400mg bid PO
- Group C: Identical appearing placebo bid PO

Treatment will be for 28 days (**Fig. 1, above**). Given variable outcomes and response to corticosteroid therapy in patients with severe AH, a Lille model was developed by French investigators to identify subjects early in the course of treatment that are unlikely to benefit from continued treatment and in fact might have worse outcome. The Lille model takes into account patient's age, and at the start of therapy total bilirubin, albumin, creatinine, prothrombin time values and total bilirubin level on day 7 of therapy. It projects a 6-month survival probability of patients with a Lille score above 0.45 to be about 25% contrary to patients with a Lille score below this cutoff (85%). Subjects who meet the Lille criteria for failure of treatment on Day 7 or side effects requiring discontinuation of steroids will be removed from the study. Standard of care nutrition support and alcohol cessation recommendations will be provided to all subjects. Alcohol withdrawal will be managed per standard of care.

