## STATISTICAL METHODS PLANNED AND SAMPLE SIZE

### Determination of Sample Size

Given the potential for changes in clinical status we used a S.D. of 25% for our sample size calculations and estimated the size required to obtain 80-90% power for changes in LPS *in placebo vs. either arm* with active drug in four difference scenarios shown in **Table 4**. Due to multiple comparisons, the p value is set at 0.025.

Table 4	Scenario 1	Scenario 2	Scenario 3	Scenario 4
$\alpha$ (p value)	0.05	0.025	0.025	0.025
power (%)	90	80	90	90
placebo mean/SD drop in LPS (%)	25/10	25/25	25/25	25/25
Imm-124 E mean/SD drop in LPS at either dose (%)	50/10	50/25	70/25	50/25
N required (each group)	5	20	7	26

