### **Null Hypothesis**

The null hypothesis is that there will be no significant differences between the steroid + placebo arm, versus either steroid + active drug arm, with respect to the plasma endotoxin level.

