### **Analysis Population**

For the mechanistic endpoints, we will perform an intent-to-treat analysis. An intent to treat analysis will also be performed for the following endpoints:

- Proportion meeting Lille criteria for futility (Lille score > 0.45)
- Mortality at day 30, 90 and 180
- Change in MELD score and discriminant function adjusting at day 7 and 30 for baseline values
- Change in liver functions adjusting for baseline values on day 7 and 30.

For mechanistic and safety related endpoints, we will include an efficacy evaluable set which will only include those who have received drug for the planned duration within the study.

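### Endotoxin has two unreconciled analysis populations, and its Day 28 ITT comparison stands only if removed patients are still sampled

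*Combined protocol and SAP*

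**What the plan says.** **Role of endotoxin.** In Determination of Sample Size the sponsor "estimated the size required to obtain 80-90% power for changes in LPS". The Null Hypothesis section compares placebo "versus either steroid + active drug arm, with respect to the plasma endotoxin level", and names no other endpoint. The Synopsis lists endotoxin first among the mechanistic endpoints and describes the sizing measure as a "decrease in plasma endotoxin levels (adjusting for baseline) as measured by analysis of covariance across the study groups". Subject Disposition calls it the principal secondary endpoint. Secondary Endpoints places the comparison at Days 7 and 28. Interpretation of Labs, the section on other mechanism-related endpoints, and Subject Disposition disclaim formal testing for cytokines, microbiome, permeability and adverse events.

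**Populations.** Analysis Population says: "For the mechanistic endpoints, we will perform an intent-to-treat analysis". It then adds, for mechanistic and safety endpoints, an efficacy evaluable set that "will only include those who have received drug for the planned duration within the study". Subject Populations, the next section, says that "those who receive at least 7 days of treatment will be considered for the primary pathophysiology-based endpoint".

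**Removal and follow-up.** Under Overall Study Design and Plan, patients who meet the Lille criteria "for failure of treatment on Day 7 or side effects requiring discontinuation of steroids will be removed from the study"; Removal of Subjects from Therapy or Assessment repeats this for Lille failures. Yet the ITT list in Analysis Population includes "Change in MELD score and discriminant function adjusting at day 7 and 30 for baseline values", liver function at the same days, and mortality to Day 180.

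**Sampling and missing data.** Table 2 draws endotoxin at D0, D7 and D30 only. The tests listed at withdrawal do not include it. Subject Disposition rules out replacing missing values by estimates.

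**The concern.** Two sections in force side by side define different patients for the same comparison, and no rule says which counts. The 7-day threshold also falls on the day Lille failures are removed, so whether they meet it depends on how days are counted.

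The larger issue is Day 28. If removal means no further assessment, Lille failures have no later endotoxin value and nothing stands in for it. An ANCOVA reported as ITT would then be an analysis of patients retained after Day 7. Retention depends on early response, which is itself a trial endpoint that the drug may change, so the contrast would no longer compare the groups as randomised. Endotoxin is secondary in a Phase 2a study, but it is the mechanism test that sets the sample size.

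**Working it through.** **1. Which populations conflict.** ITT keeps every randomised patient. The 7-day rule drops those who stopped earlier. Both are assigned without a hierarchy, which is the conflict. The full-duration set is worded as an addition to ITT and is not a conflict in itself.

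**2. The plan's own figure.** Inputs from Table 4: difference 25 points (45 in Scenario 3), SD 25 (10 in Scenario 1), alpha 0.025 (0.05 in Scenario 1), power 80-90%; two-sided tests from Safety Analysis. Formula: n = 2(SD/difference)²(z for alpha/2 + z for power)².
- Scenario 2: 2 × 1 × (2.241 + 0.842)² = 19.0, so 20 (stated 20).
- Scenario 4: 2 × 1 × (2.241 + 1.282)² = 24.8, so 25 (stated 26).
- Scenarios 1 and 3 give 4 and 8 (stated 5 and 7).

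All four agree within one patient. At the chosen 22 per arm, a two-sample t-test (noncentral t) has 83.5% power, inside the stated range, provided all 22 contribute a value.

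**3. Day 7.** Assume no true endotoxin effect, and that the endotoxin drop correlates (rho) with Lille response. If a fraction f with the worst response is left out, the mean drop in the rest rises by 25 × rho × L(f), where L(f) is the mean of a standard normal variable above its f quantile: L(0.20) = 0.350, L(0.30) = 0.497, L(0.40) = 0.644. With 40% failure on placebo:
- f = 0.30 on drug, rho = 0.3: 25 × 0.3 × (0.497 − 0.644) = −1.1
- f = 0.20 on drug, rho = 0.5: 25 × 0.5 × (0.350 − 0.644) = −3.7

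A negative value counts against the drug. This applies only if Lille failures are held *not* to have 7 days of treatment. Counted as D0 to D6 they do have 7 days, they stay in the set, and this bias is 0.

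**4. Day 28, retained patients only, if removal ends assessment.** If Day 28 endotoxin relates to Lille response directly, the same formula gives −1.1 to −3.7. If it relates only through Day 7, multiply by an assumed Day 7-Day 28 correlation of 0.5 or 0.7, which gives −0.55 to −2.6. The overall range is about 0.6 to 3.7 points against the drug. For scale, the standard error at 22 per arm is 25 × √(2/22) = 7.5, so the largest value is about half a standard error (3.7/7.5 = 0.49).

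**5. What a repeated-measures model does.** In simulation under the same assumptions (20,000 trials per case), a maximum-likelihood analysis using Day 7 values has bias within 0.1 point if Day 28 values are missing at random given Day 7, and 0.4 to 2.1 points against the drug if they are not.

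**6. Power if patients are lost at Day 28.** This is a consequence of removal, not a measure of the population conflict. The documents give no loss rate. The third column uses Day 7 values, with correlation 0.5 / 0.7 (8,000 simulated trials per case, loss at random).

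| Per arm at Day 28 | Assumed loss | Retained-only power | Repeated-measures power |
|---|---|---|---|
| 22 | 0% | 83.5% | – |
| 18 | 18% | 74.1% | 75.6 / 77.8% |
| 15 | 32% | 64.6% | 67.2 / 71.6% |
| 13 | 41% | 56.9% | 60.9 / 65.6% |

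**7. Separate point on laboratory values.** The residual variance of ANCOVA relative to ANOVA on changes is (1 − r²)q²/(1 + q² − 2rq), with r the baseline-follow-up correlation and q the follow-up/baseline SD ratio. At q = 1 and r = 0.3/0.5/0.7 the ratio is 0.65/0.75/0.85, a variance 35/25/15% lower. With q between 0.8 and 1.25 the reduction runs from 2% to 50%.

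**The case against.** A reader might infer that the Day 28 comparison *cannot* be ITT. The documents do not support that. ITT analysis of MELD, discriminant function and liver function at Day 30, and of mortality to Day 180, implies that removed patients are still seen, and Table 2 puts the endotoxin draw at the same D30 visit. On that reading the sample could be taken. What stands is that the removal text says the opposite, no text says endotoxin is drawn after removal, and an early discontinuation visit held at Day 7 cannot supply a Day 28 value.

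A reader might also infer that the planned duration of the evaluable set is undefined. It is 28 days, in the Synopsis and in Study Procedures; only a tolerance for missed doses is absent.

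At Day 7 the practical effect is probably small. On an ordinary count Lille failures qualify, and many patients who stop earlier through death or withdrawal would have no Day 7 sample under either rule. By the same token, even the Day 7 ITT analysis is complete only for those sampled.

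Finally, the bias figures pair no endotoxin effect with a clear Lille benefit, although the proposed mechanism acts through LPS. That is fair: they illustrate scale and do not predict. The conflict in the text does not depend on them.

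**Conclusion.** The concern holds in this form: endotoxin has two unreconciled populations with none named primary, and its Day 28 ITT label is accurate only if removed patients are still sampled at D30, on which the plan contradicts itself. Reading the 7-day endpoint as endotoxin is an inference from its role in the sizing and the null hypothesis, since the term is not defined.

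The size is modest. If removal ends assessment, the Day 28 bias is roughly 0.6 to 3.7 points under assumed failure rates and correlations. It would be zero with equal failure rates in this model, and would reverse in sign if the drug worsened Lille response. The loss of power could matter more, but it too depends on an unstated loss rate. This should be corrected before analysis; it does not undermine the safety objective, which is the primary endpoint.

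**What to change.** 1. Name all randomised patients, analysed as randomised, the primary endotoxin population. Make the 7-day and full-duration sets supportive only, and state the tolerance for missed doses in the latter.
2. Analyse all observed Day 7 and D30 values (the D30 draw serving as the Day 28 value) in a baseline-adjusted repeated-measures model with arm, visit and arm-by-visit, and read each dose-versus-placebo contrast from it. This imputes nothing, so it respects Subject Disposition. State the missing-at-random assumption, report the numbers contributing and the deaths by arm at each visit, and say how deaths before Day 28 are handled; a supportive rank analysis with deaths ranked worst is one option.
3. Reconcile the removal text with the Day 30 and Day 180 ITT promises. If removed patients are still assessed at D30, include their endotoxin sample; that is the only route to an observed Day 28 ITT comparison.
4. Separately, and not about endotoxin populations: replace ANOVA on laboratory changes (Synopsis, Safety Analysis) by ANCOVA on baseline, in line with Analysis Population and Anticipated Outcomes, and align the Synopsis ANOVA line for secondary endpoints with the endotoxin ANCOVA stated elsewhere.

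**Cost.** Wording and one more model, with no new patients and no change to treatment or removal rules. The downside is reliance on missing at random, with only a small gain in power (about 2 to 9 percentage points). Item 3 would add at most 3 × 4 = 12, 3 × 7 = 21 or 3 × 9 = 27 samples of 66 at the losses assumed above, fewer if some of those patients have died or withdrawn.

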### **Subject Disposition**

Missing values will be explained in individual data tables. No procedures for replacing missing values by estimates will be implemented.

If there is scientific evidence or explanation for one or more outliers, this will be presented together with a statistical test for outlier identification. In case of outliers, the corresponding statistical analysis will be provided with and without these values.

Any deviation from the original statistical plan will be described and justified in the study report.

**Primary endpoint:** The incidence and severity profile of adverse events will be reported for those receiving Imm-124 versus placebo. It is expected that there will be no signals for increased adverse events with Imm-124. The adverse event rates will be enumerated for each group. Proportions of subjects with specific adverse events will be compared using Fisher Exact test. However, no formal hypothesis testing is planned as there is no basis to expect any changes across groups.

**Principal secondary endpoint:** The principal secondary endpoint will be the decrease in plasma LPS (endotoxin) levels (adjusting for baseline) as measured by analysis of covariance across the study groups. This was chosen based on the mechanism of action of Imm 124-E. The hypothesis is that both active-drug groups are superior to placebo. In prior studies, we have found the standard deviation of LPS levels to be 8-10%.

**Subgroup Analysis:** We will perform subgroup analysis based on gender, race, baseline MELD and SOFA scores, and presence or absence of encephalopathy. Given the overall sample size, we do not anticipate having enough power to do meaningful hypothesis testing. We will also do

a multivariable regression analysis of outcomes with these as covariates to determine if they have an independent impact on outcome, and to identify any interaction terms between these covariates and treatment arm. These are primarily designed for hypothesis generation.

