### **Removal of Subjects from Therapy or Assessment**

Each subject will be informed of their right to withdraw from the study at any time and for any reason. Subjects may be withdrawn from treatment or assessment:

- If continuing in the study does not appear to be in the best medical interest of the subject, his/her participation may be terminated by either the Principal Investigator or the study director. Removal of an individual by the Principal Investigator will be reported to the Institutional Review Board and the appropriate regulatory agencies according to the guidelines of these groups.
- Subjects considered as treatment failure i.e. those who meet Lille criteria for failure will be removed from the study and will be offered alternative standard therapy by their treating physician.

Reasons for permanent discontinuation include the following:

- The subject decides to withdraw from the study.
- The Investigator may withdraw a subject from the study at any time if he considers that remaining in the study compromises the subject's health or the subject is not sufficiently cooperative.
- The study DSMB on behalf of NIH and the TREAT consortium may ask that a subject be withdrawn from the study if it considers that remaining in the study compromises the subject's health and after discussing the issue with the Principal Investigator.

The reasons for any subject withdrawal will be recorded on the study completion form of the case report form (CRF). The Investigator will inform the Sponsor in writing of the subject's early withdrawal for any reason.

Upon withdrawal from the study, any time after dosing has taken place, the subject will have a further hematology, serum biochemistry, urinalysis, and medical examination. Laboratory tests will be those outlined for the follow-up safety tests in Appendix 1.

If withdrawal is caused by an adverse event that the Investigator considers may be related to the Imm 124-E, it will be reported to the IRB and to the Sponsor.

Any serious unexpected adverse event which is thought to be possibly or probably related to the study drug must be reported to Sponsors by telephone within 24 hours of being informed of the SAE or on the next business day after a holiday or weekend, and then, a Serious Adverse Event form must be completed and faxed to the sponsors within 48 hours. The event must be reported to the IRB within 5 days.

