## Adverse Events

### **Adverse Events (AE), Serious Adverse Events (SAE), and Suspected Adverse Reactions**

An adverse event (AE) is any untoward medical occurrence in a subject participating in a clinical trial. An adverse event can be any unfavorable and unintended sign, symptom or disease temporally associated with the use of the study medication, whether or not considered related to the study medication. AEs will be collected from the start of treatment until 24 weeks following the initial dose of study medication. Any events occurring prior to treatment will be recorded on the medical history page with the event name, onset date and end date if not continuing. Pre-existing, known clinically significant conditions observed at screening should be recorded as medical history.

This definition also includes accidental injuries, reasons for any change in medication (drug and/or dose) other than planned titration, reasons for admission to a hospital, or reasons for surgical procedures (unless for minor elective surgery for a pre-existing condition). It also includes adverse events commonly observed and adverse events anticipated based on the pharmacological effect of the study medication.

A **treatment emergent adverse event** is any adverse event occurring after start of study medication and within the time of residual drug effect, or a pre-treatment adverse event or pre-existing medical condition that worsens in intensity after start of study medication and within the time of residual drug effect.

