## **Safety Analysis**

Safety will be assessed by descriptive statistics of AEs and laboratory tests. The incidence of reported AEs and the values of laboratory tests from all subjects will be presented with and without regard to causality based on the Investigator's judgment.

Adverse events will be coded according to MedDRA and presented in tables by system organ class, MedDRA preferred term and study group. Adverse events will be summarized by treatment group to provide visual comparison among the treatment groups with respect to incidence of adverse events (the number of subjects reporting at least one episode of a specific adverse event), incidence of adverse events by severity within body system, incidence of adverse events by attribution within body system, and incidence of adverse events causing withdrawal and incidence of serious adverse events. Regarding severity and attribution summaries, the most extreme outcome (highest severity and closest to study drug related) will be used for those subjects who experience the same adverse event on more than one occasion.

Written narratives will be provided for all serious, unexpected or other significant adverse events that are judged to be of special interest because of their clinical importance.

Chi-square test or Fisher's Exact test (as appropriate) will be applied for testing the statistical significance of the difference in percent of subjects reporting adverse events between the study groups.

Paired T-Test or Signed Rank test (as appropriate) will be applied for testing the statistical significance of the changes from baseline in laboratory results within each study group.

ANOVA model will be applied for testing the statistical significance of the difference in the changes in laboratory results between the study groups. Dunnett's method will be used for comparing each of the active groups to the Placebo group. Adverse Events

All tests will be two-tailed, and a p value of  $\leq 5\%$  will be considered statistically significant.

The data will be analyzed using the SAS ® version 9.1 (SAS Institute, Cary North Carolina).

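### Adverse events are compared only as crude 24-week proportions, so unequal time at risk can dilute, or with a large mortality gap reverse, a true excess of named non-fatal events

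*Combined protocol and SAP*

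**What the plan says.** The Primary Endpoint section names the safety profile. Subject Disposition gives the comparison: "Proportions of subjects with specific adverse events will be compared using Fisher Exact test". Safety Analysis defines incidence as "the number of subjects reporting at least one episode of a specific adverse event" and prescribes a chi-square or Fisher test for "testing the statistical significance of the difference in percent of subjects reporting adverse events between the study groups".

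The denominator is in Subject Populations: "All subjects who receive at least one dose of Imm 124-E or placebo will be included in the safety analysis". The window is in the Adverse Events section: "AEs will be collected from the start of treatment until 24 weeks following the initial dose of study medication".

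Early exit is built into the design. Under Overall Study Design and Plan, subjects who meet the Lille criteria "for failure of treatment on Day 7 or side effects requiring discontinuation of steroids will be removed from the study". Removal of Subjects from Therapy or Assessment repeats this for Lille failures: "those who meet Lille criteria for failure will be removed from the study and will be offered alternative standard therapy by their treating physician".

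Neither the safety sections nor the rest of the document gives a person-time rate, a time-to-event or cumulative-incidence method, or a censoring rule for AEs. Subject Disposition does say that AE rates will be enumerated, but the definition in Safety Analysis makes these counts of subjects.

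**The concern.** A subject who dies in week 2, or whose AE collection stops at day 7, cannot contribute a later first episode of sepsis, renal failure or encephalopathy, yet stays in the denominator. If deaths or removals differ between arms, the arm that loses more observation time tends to show a lower proportion at the same underlying event rate.

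The documents make unequal exposure plausible. Current Treatment cites mortality above 40% in severe disease, without a time horizon. The design section cites six-month survival of about 25% above the Lille cutoff and 85% below it. Lille failure is itself an exploratory endpoint, so a drug that changes it also changes time under observation. A beneficial drug could look more toxic at an identical event rate, and a harmful one less so.

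The second safety set under Analysis Population does not repair this. It keeps only subjects dosed for the planned duration, so early deaths and removals drop out.

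**Working it through.** **Inputs.** From the documents: 22 per arm, 24 weeks (168 days) of AE collection, 28 days of dosing, possible removal at day 7. They give no arm-specific rates of death, removal or AEs and no calculation for the AE comparison, so there is no plan figure to reproduce. All rates below are assumptions, with AE and death hazards independent.

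**1. Equal AE hazards, unequal deaths.** Crude incidence = λ/(λ+μ) × [1 − exp(−(λ+μ)·24)], in weeks. Take λ = ln 2/24 = 0.0289, which gives 50% over a full 24 weeks. Take μ = −ln(1−D)/24 for D the 24-week mortality.
- D = 20%: μ = 0.0093; 0.7565 × (1 − 0.5 × 0.8) = 45.4%, or 10.0 of 22.
- D = 40%: μ = 0.0213; 0.5757 × (1 − 0.5 × 0.6) = 40.3%, or 8.9 of 22.
- D = 60%: 34.5%.
- With λ set to give 30% instead of 50%, D = 20% and 40% give 27.1% and 23.8%.

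The true rate ratio is 1.0 throughout.

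**2. Equal AE hazards, unequal removal at day 7, AE collection stopping there.** Crude incidence = f(1 − e^(−λ)) + (1−f)·0.5, where 1 − e^(−0.0289) = 0.0285.
- f = 20%: 0.0057 + 0.4 = 40.6%.
- f = 40%: 0.0114 + 0.3 = 31.1%.

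On treatment only, at 0.03 per day, subjects with 28 days have 1 − e^(−0.84) = 56.8% and subjects with 7 days have 1 − e^(−0.21) = 18.9%. For f = 20% this gives 0.8 × 56.8% + 0.2 × 18.9% = 49%. For f = 40% it gives 0.6 × 56.8% + 0.4 × 18.9% = 42%.

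**3. A true excess on active.** AE hazard 0.005 versus 0.004 per day (ratio 1.25), with 60% of deaths by day 30. Then μ1 = −ln(1−0.6D)/30 up to day 30, and μ2 = −ln[(1−D)/(1−0.6D)]/138 after it. Crude incidence = λ/(λ+μ1)·(1−e^(−30(λ+μ1))) + e^(−30(λ+μ1))·λ/(λ+μ2)·(1−e^(−138(λ+μ2))). Placebo mortality is fixed at 20% (μ1 = 0.00426, μ2 = 0.00069), which gives 42.3% on placebo.

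| Active mortality | Crude, active | Crude, placebo |
|---|---|---|
| 20% | 49.3% | 42.3% |
| 30% | 45.5% | 42.3% |
| 35% | 43.6% | 42.3% |
| 40% | 41.7% | 42.3% |
| 45% | 39.7% | 42.3% |

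The excess shrinks steadily and reverses near 40% versus 20%. At 45% versus 20%, the proportion with the event or death is 1 − e^(−0.84) × 0.55 = 76% versus 1 − e^(−0.672) × 0.80 = 59%, so it keeps the direction.

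**4. When AEs come early.** If all AE hazard falls in the first 4 weeks (50% over those weeks), 20% versus 40% deaths change the crude figure only from 49.2% to 48.2%.

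**5. Does one 24-week rate solve it?** Let the AE hazard be 0.02 per day to day 28 and 0.001 after, identical in both arms, with mortality 45% versus 20% as in step 3. First events per subject are 0.4243 versus 0.4692, and mean days at risk are 66.5 versus 83.1. The rates are 0.00638 and 0.00565, a ratio of 1.13 where the truth is 1.0. With a later hazard of zero the ratio is 1.16. In this example the hazard is constant within each window, so rates split at day 28 recover 1.0.

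**The case against.** The strongest reply is that deaths are not hidden. Mortality is analysed by intent to treat at days 30, 90 and 180, death meets the SAE definition, SAEs are tabulated with narratives, and a DSMB reviews safety. In the extreme example the plan would show about 10 versus 4 deaths in 22 (0.45 × 22 and 0.20 × 22). All of this stands. A reader might infer that the arm with more deaths would pass as the safer one overall; the documents do not support that. Nor is every between-arm safety comparison a crude proportion: laboratory changes are compared by ANOVA with Dunnett's method. The point is confined to named non-fatal AEs.

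Second, with complete follow-up to death the crude proportion is a valid cumulative incidence with death as a competing event. That also stands. The weakness is reading it alone, plus an undercount wherever AE collection stops at removal.

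Third, a fatal sepsis or renal failure is itself a counted event, so AEs that precede death could offset or reverse the effect. The independence assumed above favours the concern.

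Fourth, the cited mortality is for severe disease in general, whereas this trial caps MELD at 28 and excludes active infection, creatinine above 1.5 mg/dL and active bleeding. Small samples also mislead in their own right. In simulated 22 versus 22 trials with the 25% excess and equal 20% mortality, the crude comparison already points the wrong way in 27%. At 45% versus 20% it does so in about 50%, and the 24-week rate in about 32%.

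Fifth, the plan calls the comparison descriptive. Only part of this stands: Subject Disposition disclaims formal testing, but the same paragraph and Safety Analysis prescribe tests, the latter with a 5% threshold. A description also needs the right denominator.

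**Conclusion.** The gap is real and modest. Between-arm AE comparisons have no time-at-risk element, while deaths and day-7 removals can make time at risk unequal. With equal hazards the arm with more deaths or removals shows a proportion about 1 to 11 percentage points lower in the scenarios run, and about one subject in 22 lower at 20% versus 40% deaths. A true 25% excess is diluted at smaller mortality gaps and reverses only at about 40% versus 20% or more. This assumes constant, independent hazards in step 3, and arm-specific rates that the documents do not give. If events cluster in the first weeks, the effect of deaths is small.

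A reader might also infer that person-time rates should replace the crude table as the basis for the safety conclusion. Step 5 shows why not: a single 24-week rate is itself biased when the hazard changes over time. Label: cheap improvement.

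**What to change.** In Subject Disposition and Safety Analysis, keep the crude table. For sepsis, renal failure, encephalopathy, pulmonary compromise, gastrointestinal events and SAEs, add:

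1. Patient-days at risk per arm and first-event rates, with rate ratio and 95% CI for each dose versus placebo. Report these separately for the on-treatment window (to 7 days after the last dose, matching the Causality Assessment section) and for later follow-up.
2. The proportion of subjects with the event or death.

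State that the crude, windowed-rate and event-or-death results are interpreted together with mortality, and that no conclusion rests on the rates alone.

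Reconcile the passages on removal from the study with the 24-week AE window: say whether AE collection continues to week 24 after removal. Censor time at risk at the end of AE collection. Without this rule, time at risk in later follow-up is undefined.

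The cost is SAP wording and a few more safety tables, since AE start dates and deaths are already to be recorded. The rate ratios will have wide intervals at 22 per arm.
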